	Mayo full clinical score	X			X			X		
	Mayo partial clinical score		X ^q	X			X			
	Patient diary to support mayo clinical score	X	X	X	X		X	X		
	Colonic biopsy	X			X			X		

Key: ALC = absolute lymphocyte count; ET = Early Termination; IP = Induction Period; MP = Maintenance Period; OCT = optical coherence tomography; OLP = Open-Label Period; PD = pharmacodynamic; PK = pharmacokinetic; TB = tuberculosis; WOCBP = women of child-bearing potential.

Footnotes to Table 1

- a. The duration of Visit 1 will be approximately 7 hours. Prior to dosing a 12-lead ECG will be performed and following dosing patients will have hourly vital signs recorded at 1, 2, 3, 4, 5 and 6 hours (± 10 minutes) postdose. A further 12-lead ECG will be performed at the end of the observation period.
- b. Study visits should be scheduled in the morning, where possible, and on study visit days patients should be instructed to withhold the dose until the study visit and the dose should be administered during the visit.
- c. Just prior to dosing at Visit 1, patients will begin 24-hours of Holter monitoring. Patients will not be expected to remain on site for the 24-hour duration as monitoring will continue at home.
- d. IP Week 4 and IP Week 8 occur 4 and 8 weeks, respectively, following the completion of dose escalation, ensuring 8 weeks of dosing at the assigned dose.
- e. Medical history will include smoking history. The Day 1 medical history can be abbreviated, noting events that occurred between Screening and Day 1.
- f. Screening for TB will include a review of past history, current physical exam. A chest X-ray will be obtained for those subjects who do not have a chest X-ray within 6 months prior to screening and either a tuberculin skin test or a QuantiFERON[®] gold test for TB.
- g. Serology testing will be performed at screening to determine the patient's immune status with respect to the following viruses: varicella zoster virus (VZV), human immunodeficiency virus (HIV) antibodies, hepatitis B surface antigen (HBsAg) and anti-hepatitis B core antigen (HBcAg) IgM, anti-hepatitis C virus (HCV) IgG or IgM, should be assessed at screening in all patients.
- h. At screening the stool sample should be used to rule out serious infection and should include evaluation for *C. difficile* toxin as well as ova and parasitic examination.

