2 Begin at least 15 minutes predose and continue for 24 hours after dose.

3 Holter monitoring will be performed on Day 1/IOLP.

4 See Section 9.6.7.2 for discharge criteria. Additional observation should be instituted until the finding has resolved in the following situations: HR 6 hours post-dose is < 45 bpm; HR 6 hours post-dose is at the lowest value post-dose; ECG 6 hours post-dose shows new onset second degree or higher AV block; the ECG 6 hours post-dose shows a prolonged QTcF interval (> 450 msec males, > 470 msec females).

There is no provision for dose adjustments in this study. Patients who cannot tolerate investigational drug must be withdrawn from the study.

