10.3. Induction Period (IP) and Maintenance Period (MP)

Eligible patients will be randomized to treatment group on Day 1. Visits, assessments, and procedures will be performed as per the Schedule of Events in [Table 1](#). Guidelines for dose escalation (Day 1) are provided in [Section 9.6.7](#).

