- (1.25 mg dose) MS clinical studies. Nonclinical studies with RPC1063 have not revealed eye-related toxicities. In this study, OCT will be performed in all patients at baseline and the end of study visits or early termination. In addition, patients will be questioned about visual signs or symptoms at each study visit and instructed to inform the investigator if they develop symptoms between visits. For patients with symptoms of macular edema, OCT and ophthalmologic examination including dilated ophthalmoscopy will also be performed. Every patient whose ophthalmic evaluations reveal abnormalities will be followed until values return to baseline.
- e. Opportunistic or serious infections. TB, serious bacterial infections, systemic fungal infections, viral infections such as herpes infections (including herpes zoster and disseminated herpes simplex) and protozoal infections should be reported as adverse events of special interest.

Overall, the following procedures should be followed:

- Vital signs will be assessed in supine and standing position at every visit. A sudden, significant fall in BP (> 20 mmHg) between 2 and 5 minutes after standing from the supine position will be interpreted as orthostatic hypotension and will be documented in the patient chart and eCRF.
- Patients will be closely monitored in the clinic after their first dose of the initial dose escalation regimen for a period of 6 hours after treatment. ECGs will occur predose and at Hour 6 following dosing, with more frequent assessments as clinically indicated; vital signs, including orthostatic BP assessment, will be assessed predose and then hourly for 6 hours following dosing.
- Clinicians should be particularly mindful of patients who have a low HR at baseline (spontaneously or through drug induced β -receptor blockade), prior to administration of the investigational drug. Atropine IV is recommended as the first line treatment of bradycardia, up to a maximum daily dose of 3 mg. Furthermore, the common guidelines for treatment of bradycardia (e.g., Advanced Cardiac Life Support-ACLS guidelines) should be followed as appropriate:
 - In case of clinical symptoms or hypotension, administration of atropine 1 mg, repeated administration in 3-5 minutes.
 - If HR and/or BP remain unresponsive, consider administration of dopamine drip 5-20 μ g/kg/min or epinephrine drip 2-10 μ g/min.
 - Performance of transcutaneous pacing may also be considered

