6.20.4. Vital Signs

Heart rate (HR) and systolic/diastolic blood pressure (BP) will be assessed at scheduled times as outlined in protocol.

After the patient has been supine for at least 15 minutes, HR and BP will be measured 3 times using an automated validated device. The repeat HR and BP measurements will be made at 2-minute intervals. The lowest predose HR and BP (based on Systolic BP) will be taken as the baseline measure and used as comparison to postdose values. BP will then be measured in the same manner with the patient in the standing position. A sudden, significant fall in BP (> 20 mmHg) between 2 and 5 minutes after standing from the supine position will be interpreted as orthostatic hypotension and will be documented in the patient chart and eCRF.

After the first dose of study treatment, patients will be carefully monitored during a 6-hour post-dose monitoring period of hourly recording of HR (supine) and BP (supine and orthostatic). During the 6-hour post-dose monitoring on Day 1, after the patient has been supine for at least 5 minutes, HR and BP will be measured once using an automated validated device. Any clinically relevant change from baseline should be confirmed on repeat measures. Blood pressure will then be measured in the same manner with the patient in the standing position. The same orthostatic hypotension criteria stated above will be applied.

Heart rate and systolic and diastolic blood pressure will be summarized using descriptive statistics at each timepoint by treatment group. BP measurements will be summarized separately in the supine and orthostatic positions. Any clinically significant changes will be recorded as AEs or SAEs.

For patients participating in cardiac monitoring on Day 5, a summary table will be provided that summarizes the hourly change from pre-dose assessment through hour 6 at each of the baseline and Day 5, visits by treatment group for heart rate and blood pressure.

Box plots will be provided to display the distribution of HR and BP. In addition, line plots will be created to display the change from baseline over the entire study period and change from pre-dose in HR and BP for the baseline and Day 5visits.

The number and percentage of subjects with clinically relevant abnormalities will be presented by treatment group. The criteria for clinically relevant abnormalities are shown in the following table.

Table 1. Criteria to Determine Clinically Relevant Abnormalities in Vital Signs

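### SAP 6.20.4 admits only patients with Day 5 monitoring to its hourly-change table, so hourly Day 1 change in heart rate and blood pressure is not summarised numerically for the whole Safety population

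*SAP*

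**What the plan says.** SAP 6.20.4 (Vital Signs) defines the table in one sentence. It begins "For patients participating in cardiac monitoring on Day 5, a summary table will be provided that summarizes the hourly change from pre-dose assessment" and continues "through hour 6 at each of the baseline and Day 5, visits by treatment group for heart rate and blood pressure". The opening condition therefore governs both visits in the table.

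The same section also plans, without that condition:

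- summaries of actual values: "Heart rate and systolic and diastolic blood pressure will be summarized using descriptive statistics at each timepoint by treatment group";
- box plots, and line plots that include change from pre-dose at the baseline and Day 5 visits;
- a count and percentage, by treatment group, of patients crossing limits set in SAP Table 1, some of which are changes from pre-dosing;
- listings of every vital-sign measurement.

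SAP 6.20 makes the Safety population the default for all safety summaries and rules out hypothesis tests on safety results.

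In the protocol, footnote a to Table 1 applies to every patient at Visit 1: "following dosing patients will have hourly vital signs recorded at 1, 2, 3, 4, 5 and 6 hours". Section 11.5 ties the in-clinic observation to the first dose: "Patients will be closely monitored in the clinic after their first dose of the initial dose escalation regimen for a period of 6 hours". Footnote 3 to Table 4 (cardiac monitoring during dose escalation) reads "Holter monitoring will be performed on Day 1/IOLP".

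**The concern.** Slowing of the heart rate and conduction abnormalities are named adverse events of special interest, and Protocol 11.5 describes the bradycardia seen with a related drug as dose-related, transient and mainly a first-dose effect. Within-patient change over the first six hours, by arm, is the direct summary of that effect.

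The SAP makes entry to the Day 1 half of that summary depend on something that happens afterwards: attending Day 5 monitoring. Selecting Day 1 data on a later event can only lose patients. Those lost may include people who stopped in the first four days because they did not tolerate the drug. The rule also departs from the SAP's own Safety-population default without giving a reason.

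**Working it through.** The plan states no figure for this point, so the check is mainly a comparison of the texts.

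**1. Who has the data.** Every patient dosed at Visit 1 has a pre-dose reading and readings at hours 1 to 6 (Protocol Table 1 footnote a, Table 4, Section 11.5; SAP 6.20.4 agrees). A Day 1 change table for everyone needs no new data.

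**2. Who enters the table.** Only patients with Day 5 cardiac monitoring. A patient who stopped on Days 1 to 4 cannot qualify under any version of the schedule.

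**3. Whether Day 5 monitoring is scheduled.** Protocol Table 1 goes from Day 1 to Day 36. Table 4 has columns for Day 1 and Day 1 of the open-label period only. Section 10.3 attaches the escalation guidance to Day 1 ("Guidelines for dose escalation (Day 1) are provided in" Section 9.6.7). No readable passage of the protocol mentions Day 5 monitoring.

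**4. What the other outputs supply for all patients.**

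| Output (SAP 6.20.4) | Limited to Day 5 patients? | Numerical summary of hourly within-patient change? |
|---|---|---|
| Hourly-change table | Yes | Yes |
| Descriptive statistics by timepoint | No | Not stated; actual values |
| Limit-crossing counts (heart rate down or up by more than 20 bpm; systolic down by more than 30 or up by more than 40 mmHg; diastolic down or up by more than 30 mmHg) | No | No; counts only, and not stated to be by hour or for Day 1 alone |
| Line plots of change from pre-dose | Not expressly | No; a figure |
| Listings | No | No |

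The SAP names change explicitly where it wants it tabulated elsewhere: ECG (6.20.5), blood counts (6.20.6), pulmonary function (6.20.7) and lymphocyte count (6.21). The timepoint sentence for vital signs does not.

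**5. What can be recovered by subtraction.** With complete data, mean change at hour h = mean at hour h − mean pre-dose, provided the pre-dose summary uses the same lowest-of-three value that SAP 6.20.4 sets as baseline. The spread cannot be recovered. SD of change = √(s_h² + s_0² − 2·r·s_h·s_0), where s_h and s_0 are the SDs at hour h and pre-dose, and the within-patient correlation r is not reported. If the two SDs are equal to s, this is s·√(2(1 − r)), which runs from 0 at r = 1 to 1.41s at r = 0. The median and range of change cannot be derived either.

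**6. Size.** Let f be the share of patients with Day 5 monitoring. The documents do not give f.

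- Share left out of the Day 1 half = 1 − f, anywhere from 0% to 100%.
- Loss of precision: the standard error of the Day 1 mean change grows by 1/√f. With about 60 per arm: f = 25% (15 patients) gives 2.0; f = 50% (30) gives 1.41; f = 75% (45) gives 1.15.
- Bias, for illustration only: suppose a share q of an active arm stops on Days 1 to 4 after a mean fall D, and the rest fall by d on average. The full-arm mean is qD + (1 − q)d, and the restricted table shows d. Assuming D = 25 bpm and d = 8 bpm, q = 2% gives 0.02 × 25 + 0.98 × 8 = 8.34, and q = 5% gives 0.05 × 25 + 0.95 × 8 = 8.85, against 8.0 in the table. The understatement is 0.34 to 0.85 bpm. None of q, D or d comes from the documents.

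**The case against.** The strongest reply is that no safety signal is lost. A patient who falls by 25 bpm and stops on Day 2 is still counted in the row for falls of more than 20 bpm, contributes to the hourly values and appears in the listings. If the event is clinically significant, it is also recorded as an adverse event; bradycardia is summarised as an event of special interest, and events leading to drug discontinuation are tabulated. This stands. A reader might infer that Day 1 change is not tabulated at all, or that the largest falls vanish; the documents support neither.

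A reader might also infer that the table would hold none of the roughly 180 patients. That follows only if the current protocol schedule applied to everyone. The main SAP appears to belong to an earlier protocol version: it has 30-day follow-up and an open-label period ending when the last entrant reaches 20 weeks, where the protocol has 90 days and up to 6 years. Protocol visit numbers jump from Visit 1 to Visit 4, and text in the escalation guidance is blacked out. Some or many patients may have had Day 5 monitoring. This also stands, so a claim that most or all patients are excluded cannot be made.

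Third, the table can be read as a paired Day 1 and Day 5 display. Under the 4-day and 3-day steps in SAP Section 4, Day 5 is the first day at 0.5 mg, and limiting a paired display to patients with both days is ordinary practice. That justifies the paired table. It does not justify leaving the full population without an unpaired Day 1 table.

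Last, there are no safety tests, so the precision ratios have no inferential consequence, and SAP 6.10 allows further analyses for the study report. Both are true and keep the point minor. An analysis added later would, however, have to be labelled as unplanned.

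**Conclusion.** The point holds in a narrow form. The only numerical table of hourly change from pre-dose that SAP 6.20.4 names selects its Day 1 data on a later event, and the readable protocol does not schedule that event. The gap is a numerical summary (mean, SD, median, range) of within-patient hourly Day 1 change for the whole Safety population. Threshold counts, hourly values, plots and listings remain for everyone.

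The excluded share is unknown, from 0% to 100%, and the bpm figures above rest wholly on assumed inputs. The conclusion assumes that the SAP sentence is applied as written and that the blacked-out protocol text does not itself schedule Day 5 monitoring. If it does, the mismatch with the schedule falls away, but patients who stopped before Day 5 are still excluded. The severity is minor: efficacy results and the capture of adverse events are unaffected.

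**What to change.** In SAP 6.20.4:

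1. Tabulate hourly change from pre-dose through hour 6 on Day 1, by treatment group, for all Safety population patients, with the descriptive statistics defined in SAP 6.1.
2. Keep the Day 1 and Day 5 comparison as a second table, for patients monitored on both days, with the number contributing in each arm.
3. State that the Day 1 line plot of change from pre-dose uses all Safety patients.
4. Reconcile the Day 5 reference with the protocol schedule, saying which patients had that monitoring and under which protocol version.

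The cost is a few sentences and one extra table from data already collected. No procedure or visit changes.

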6.20.5. Electrocardiograms (ECGs) and Holter Monitoring

Stand Alone/Static ECGs

Static ECGs will be captured at intervals as defined in the schedule of assessments. The 12-lead ECG will be performed after the patient has been resting quietly in a supine position for at least 15 minutes. ECGs will be captured at scheduled times as outlined in the protocol.

Summary tables including actual values and change from baseline values will be presented for ECG results. Any clinically significant changes will be recorded as AEs or SAEs.

ECG results including morphology parameters will also be listed.

Continuous 12-lead Holter Monitoring

Continuous 24-hour cardiac monitoring (12-lead digital Holter monitoring) will be captured. Holter monitoring will start at least 15 minutes prior to dose and complete at least 24 hours postdose administration. Patients should be in the supine position prior to Holter application through the capture of the static predose 12-lead ECG as well as for the acquisition of the 6 hour post dose 12-lead ECG. Holter analysis parameters will be described in the operations document.

Any clinically significant changes will be recorded as AEs or SAEs.

6.20.6. Laboratory Assessments

Laboratory tests include the following:

- Hematology red blood cell (RBC) count, total and differential WBC count (basophils, eosinophils, lymphocytes, monocytes, and neutrophils), platelet count, hemoglobin (Hgb), hematocrit, mean corpuscular volume (MCV), mean corpuscular hemoglobin (MCH), and mean corpuscular hemoglobin concentration (MCHC). Total and differential WBC counts will not be provided to the Investigator to maintain the treatment blind. These parameters and alerts for these parameters will be monitored by the PPD Safety Surveillance team.
- Blood chemistry sodium, potassium, chloride, calcium, magnesium, phosphate, blood urea nitrogen, random glucose, albumin, alkaline phosphatase, creatinine, alanine aminotransferase, aspartate transaminase, gamma glutamyltransferase, amylase, total bilirubin, conjugated bilirubin.
- Urinalysis leukocytes, specific gravity, bilirubin, blood, glucose, ketones, pH, protein, and urobilinogen
- Pregnancy test: serum beta-hCG must be performed at screening in women of childbearing potential; urine beta-hCG will be performed at each visit, and if positive, do not dose, and confirm with a serum pregnancy test.
- Coagulation panel: prothrombin time and partial thromboplastin time.
- Serology testing will be performed at screening to determine the patient's immune status with respect to several viruses; testing will be as follows:

o anti-VZV IgG

- o HIV antibodies
- o anti-hepatitis A virus IgM
- o HBsAg and HBcAg IgM
- o anti-HCV IgG or IgM

Hematology, blood chemistry, and coagulation test results will be summarized at each study visit by treatment group for visits during the IP and MP and for all patients during the OLP. Changes from Visit 1 to the End of Study Visit will be summarized by treatment group.

Subjects with abnormalities in hematology assessments, defined as absolute lymphocyte count (ALC) <200 cells/uL, absolute neutrophil count (ANC) < 500 cells/uL as well as ANC <1000 cells/uL and total WBC >20,000 cells/uL will be summarized for each treatment group.

In addition, the change and percent change from baseline in CBC with Differential will be summarized for each treatment group.

The incidence of subjects with abnormalities in Liver Function Tests (SGPT/ALT, SGOT/AST, and GGT) will be summarized overall and at each visit for each treatment group for the following categories:

- > 1 x upper limit of normal (ULN)
- $\geq 2 \times ULN$
- $\geq 3 \times ULN$
- \geq 4 x ULN
- $\bullet > 5 \times ULN$

Shift tables will summarize changes from relevant Baseline by treatment group for visits during the IP, MP, and the OLP. Changes from Day 1 to visits during the OLP will be summarized for all patients.

All clinical laboratory results will also be listed. Laboratory values that are outside the normal range will be flagged high (H) or low (L). All out of range values will be identified in the listing.

Plasma protein biomarker results (cytokines, chemokines, other inflammatory proteins) may not be available at the time of database lock and thus may be analyzed at a later time.

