9.1.1. Study Schematic and Schedule of Events

Figure 1: Study Schematic

[figure not shown]

Table 1: Schedule of Assessments and Procedures for Induction and Maintenance Periods

	Study Procedures	Screening	Induction Period (IP)			Maintenance Period (MP)			Safety Follow-up	
			Dose Escalation	Assigned Dose						
			Visit 1 ^{a,b,c}	Visit 4 ^{b,d}	Visit 5 ^{b,d}	Relapse Visit	Visit 6 ^b	End of Study Visit/ET		
			Dose Escalation Day 1	Week 4	Week 8		Week 20	Week 32		
Day -35 to 0	Dose Escalation Day 1	Day 36±3	Day 64±3	Day 1OLP	Day 148±3	Day 232±3	Last dose + 30 days ± 7 days	Last dose + 90 ± 10 days ^r		
	Informed consent	X								
	Inclusion/exclusion criteria	X	X							
	Demographics	X								
	Medical history ^c	X	X							
	TB screening ^f	X								
	Chest X-ray ^f (if not done in previous 6 months)	X								
	Total immunoglobulins (Igs) - IgA, IgG, IgM	X					X			
	Viral serology ^g	X								
	Stool culture ^h	X								
	Randomization		X							
	Dispense investigational drug		X	X	X		X			
	Administer investigational drug at clinic		X							
	Review drug compliance			X	X		X	X		
	Prior and concomitant medications	X	X	X	X		X	X	X	
SAFETY ASSESSMENTS	Adverse events	X	X	X	X		X	X	X	
	12-Lead ECG	X	X ^a		X		X			
	Holter monitoring		X							
	Vital signs	X	X ^a	X	X		X			
	Clinical laboratory tests									
	Hematology ^s	X	X	X	X		X	X		
	Blood chemistry	X	X	X	X		X	X		

Patients not in response or who do not maintain response within this time period should follow the assessments and timings provided in the OLP table (Table 2)

	Study Procedures	Screening	Induction Period (IP)			Maintenance Period (MP)			Safety Follow-up	
			Dose Escalation		Assigned Dose					
			Visit 1 ^{a,b,c}	Visit 4 ^{b,d}	Visit 5 ^{b,d}	Relapse Visit	Visit 6 ^b	End of Study Visit/ET		
			Dose Escalation Day 1	Week 4	Week 8		Week 20	Week 32		
	Day -35 to 0	Dose Escalation Day 1	Day 36±3	Day 64±3	Day 1OLP	Day 148±3	Day 232±3	Last dose + 30 days ± 7 days	Last dose + 90 ± 10 days ^r	
	Pregnancy test (WOCBP only) ⁱ	X	X	X	X		X	X	X	X
	Coagulation panel	X						X		
	Urinalysis	X			X		X	X		
	Physical examination ^j	X	X ^k		X ^k		X ^k	X	X ^k	
	Pulmonary function tests ^l	X ^l			X ^l			X		
	Optical coherence tomography	X						X		
PK AND PD ASSESSMENTS	Stool collection for fecal biomarkers	X			X			X	X	
	Inflammatory biomarkers plasma sampling	X			X			X	X	
	PK blood sampling ^m		X	X	X		X	X	X	X
EFFICACY ASSESSMENTS	Endoscopy ⁿ	X			X ^o			X		
	Mayo scoring									
	Mayo diary	X ^p	X	X	X		X	X		

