5.1. Time Point Definitions

Study Day for Induction and Maintenance Periods

All visit data will be assigned a study day, from the Visit 1 in the Induction Period according to the following rules:

- Visit 1 Day will be designated as Day 1
- All other days after Day 1: Study Day = (Visit Date Visit 1 Date + 1)
- All other days before Day 1: Study Day = (Visit Date Visit 1 Date)

Study days for evaluations occurring during the Screening visit will be negative numbers (e.g., "-7"), no Day 0 is defined for this study.

Study Day for the Open Label Period

All visit data will be assigned a study day, from the Visit 1 in the Open Label Period according to the following rules:

- OLP Day 1 will be designated as Day 1
- All other days after OLP Day 1: Open Label Day = (Visit Date Open Label Visit 1 Date + 1)
- All other days before OLP Day 1: Open Label Day = (Visit Date Open Label Visit 1 Date)

Baseline Measurement

There will be two baseline definitions:

Baseline: The latest assessments completed prior to initial study drug administration will be used as the Baseline measurement for all analyses for the IP and MP. It will also be used as the Baseline measurement for efficacy analyses for the OLP.

Treatment Baseline: The last assessment prior to initial administration of RPC1063 will be used as the Baseline measurement for safety analyses for the OLP.

Visits

Visits identifiers on the study electronic case report forms (eCRFs) will be used.

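### The only numeric chemistry change by randomized arm in SAP 6.20.6 runs to a visit that open-label entrants do not have, and the Visit 1 starting point has no coagulation sample

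*SAP*

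**What the plan says.** SAP 6.20.6 lists these laboratory summaries:

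- Values by visit: "Hematology, blood chemistry, and coagulation test results will be summarized at each study visit by treatment group for visits during the IP and MP".
- One change summary for those same panels: "Changes from Visit 1 to the End of Study Visit will be summarized by treatment group".
- For blood counts only: "In addition, the change and percent change from baseline in CBC with Differential will be summarized for each treatment group".
- For ALT, AST and GGT, the incidence of abnormalities "will be summarized overall and at each visit for each treatment group for the following categories" (multiples of the upper limit of normal).
- Shifts: "Shift tables will summarize changes from relevant Baseline by treatment group for visits during the IP, MP, and the OLP".
- For the Open-Label Period (OLP): "Changes from Day 1 to visits during the OLP will be summarized for all patients".

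SAP 5.1 defines the reference value differently from the Visit 1 rule: "The latest assessments completed prior to initial study drug administration will be used as the Baseline measurement for all analyses for the IP and MP".

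In Protocol Table 1 (Section 9.1.1) the last on-treatment column for the Induction Period (IP) and Maintenance Period (MP) is the End of Study/ET visit, at Week 32. A note in that table reads: "Patients not in response or who do not maintain response within this time period should follow the assessments and timings" of Table 2, the OLP schedule, which closes with its own End of Open-label Visit/ET.

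**The concern.** Whether a patient has the Table 1 End of Study visit at Week 32 depends on response at Week 8 and on not relapsing afterwards. Both happen after randomization and both are what the drug is meant to change. A by-arm mean change that can be computed only for patients with that visit compares groups selected differently in each arm.

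At Week 8, chemistry is scheduled for every patient still in induction and nobody has yet been sorted by response. No numeric chemistry change is written for that visit.

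This matters most for small drifts within the normal range in analytes such as bilirubin, creatinine or albumin. Categorical shifts can miss such drifts, and the multiples-of-normal table does not cover these analytes. SAP 6.20.1 also names hepatotoxicity, assessed by blood chemistry, as an event of special interest.

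The coagulation problem is simpler: the stated starting visit has no sample.

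**Working it through.** The plan states no figure on this point to reproduce. The check sets SAP 6.20.6 beside Protocol Tables 1 and 2.

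**Step 1: what each planned output gives for chemistry.**

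| Output in SAP 6.20.6 | Covers chemistry | By randomized arm | At Week 8 | Numeric within-patient change |
|---|---|---|---|---|
| Values at each IP/MP visit | Yes | Yes | Yes | No |
| Multiples of the upper limit | ALT, AST, GGT only | Yes | Yes | No |
| Shift tables from Baseline | Yes | Yes | Yes | No (categories) |
| Visit 1 to End of Study | Yes | Yes | No | Yes |
| Day 1 to OLP visits | Yes | No (all patients together) | No | Yes |
| Change from baseline in blood counts | No | Yes | Visits not named | Yes |

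Only the fourth row is numeric, by arm and applies to chemistry.

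**Step 2: when samples are drawn (Table 1).** Chemistry: Screening, Visit 1, Week 4, Week 8, Week 20 and End of Study/ET. Coagulation: Screening and End of Study/ET only. The data for a Week 8 chemistry change are therefore collected already. A coagulation change from Visit 1 has no starting value.

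**Step 3: who contributes to the Visit 1 to End of Study row.**

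- Week 8 responders who stay in the MP to Week 32 contribute.
- Patients who stop drug without withdrawing consent contribute at whatever time they stop, because Protocol 9.7.1 asks them for an Early Termination visit and the Table 1 column serves both purposes.
- Week 8 nonresponders and relapsers who enter the OLP do not contribute.

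**Step 4: how unequal the groups could be.** The documents give no response rates, but the planning remission rates set a floor. Every remitter is a responder. A Mayo score of 2 or less from an entry score of at least 6 is a fall of at least 6 − 2 = 4 points, or 4/6 = 67%, and no subscore above 1 means rectal bleeding is at most 1. With the rates of 10% and 31% in SAP 6.5, the expected MP entrants are at least 60 × 0.10 = 6 on placebo and 60 × 0.31 = 18.6, about 19, on an active dose.

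Taking response rates purely as assumptions:

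| Assumed response, placebo / active | MP entrants of 60, placebo / active |
|---|---|
| 30% / 50% | 18 / 30 |
| 40% / 60% | 24 / 36 |
| 50% / 70% | 30 / 42 |

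Relapse lowers these counts and early terminators add to the row. The table shows only that membership would be partial and would differ by arm.

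**Step 5: the Week 8 report.** SAP 6.10 limits safety output at the primary analysis to the IP. The End of Study visit falls at Week 32, after the IP, so only patients who terminated early during induction could supply a chemistry change.

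**Step 6: can the change be read off the by-visit values?** Only approximately. The difference of two visit means equals the mean change only if the same patients are present at both visits. The spread is not recoverable either: Var(change) = Var(Visit 1) + Var(Week 8) − 2·Cov(Visit 1, Week 8), and by-visit summaries do not give the covariance.

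**The case against.** The strongest reply is that Week 8 is well covered. Values, liver-enzyme multiples and shifts from Baseline are all planned by arm at that visit, and a colleague could subtract the Visit 1 mean from the Week 8 mean. This stands. A reader might infer from the change sentence that chemistry is compared between arms only at the end of maintenance and never at Week 8, but SAP 6.20.6 does not support that. What is missing is the within-patient change and its SD.

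Three further replies have force:

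- The row is not made up purely of responders, because early terminators enter it.
- OLP entrants are not lost altogether. Their change from Day 1 is summarized, though pooled over arms and with everyone then assigned RPC1063 1 mg.
- The coagulation table would probably not be empty in practice. SAP 5.1 makes the Screening value Baseline, the shift tables use Baseline, and a programmer would probably do likewise here. The sentence as written still says Visit 1.

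It could also be argued that the End of Study visit means each patient's last visit, since a Protocol Table 2 footnote uses the term for patients moving to the extension study. SAP 6.20.9, however, lists the End of Study and End of OLP visits separately. On the wider reading, the row would combine Week 32 values with values taken after open-label active drug in former placebo patients, which is not a randomized comparison either.

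Finally, a reader might turn the smaller Week 32 numbers into a loss of precision relative to Week 8. That should not be claimed. The response rates would be assumed, fewer patients at Week 32 follows from the design, and the change proposed here does not alter that.

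**Conclusion.** The point holds in a narrow form and is minor. The one numeric chemistry change by randomized arm is tied to a visit whose attendance depends on response, although chemistry is scheduled at Week 8, before patients are sorted by response. The induction-only safety report would contain almost none of it. Taken literally, the same sentence cannot be carried out for coagulation, and it departs from the SAP's own Baseline definition.

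No endpoint, test or error rate is affected, since SAP 6.20 rules out hypothesis testing on safety results. The direction and size of any distortion cannot be stated from the documents. The conclusion rests on reading the End of Study visit as the Table 1 Week 32/ET visit, and on at least some nonresponders or relapsers taking up the OLP. Other safety domains already receive change from baseline (ECG in SAP 6.20.5, pulmonary function in 6.20.7), so its absence for chemistry looks like an oversight.

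**What to change.** Replace the Visit 1 to End of Study sentence in SAP 6.20.6 with:

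> Change from Baseline (Section 5.1) in hematology, blood chemistry and coagulation will be summarized by treatment group at each IP and MP visit with a sample, including Week 8 for hematology and chemistry. Week 20 and Week 32 rows are labelled as Week 8 responders remaining in the MP, and ET values are shown separately. Coagulation uses the Screening value as Baseline and has no Week 8 row.

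The cost is a wording change and extra rows in tables already planned. No samples, visits or case report form fields are added. The Week 32 comparison remains selected after the change. The gain there is that the label says so, and that the Week 8 row covers all randomized, treated patients with a sample.
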